#### **8.4. Multiple Comparisons and Multiplicity**

The trial includes separate Phase 2 and Phase 3 cohorts, where the cohorts constitute independent sets of patients. Therefore, the Phase 2 analysis has no impact on the Type I error rate for the Phase 3 analysis.

The Phase 3 cohort includes a family of hypothesis tests following the first year of treatment and a second family of hypothesis tests following the second year of treatment. All endpoints tested at Year 1 will use a significance level of 0.025 and those tested at Year 2 will also use a significance level of 0.025. Within each year, endpoints are tested following a fixed-sequence hierarchical testing strategy. Formal testing in the sequence may proceed so long as statistically significant evidence of benefit continues to be shown. At such point in the sequence that one endpoint does not show statistically significant evidence of benefit, formal statistical testing of subsequent endpoints will not occur.

Testing endpoints in the following sequence protects the overall type I error rate of 0.05 for the study:

##### **Year 1 Testing Sequence (all significance levels = 0.025)**

1. eGFR at Week 48 (primary at Year 1)
2. eGFR at Week 52 (key secondary at Year 1)

##### **Year 2 Testing Sequence (all significance levels = 0.025)**

1. eGFR at Week 100 (primary at Year 2)
2. eGFR at Week 104 (key secondary at Year 2)

3. time-to first kidney failure composite (exploratory at Year 2)
4. distribution of PGIC at Week 100
5. distribution of CGI-I at Week 100

All remaining endpoints are considered “Exploratory” and presented with nominal significance levels for descriptive purposes only.

## **8.5. Handling of Missing Data**

Missing data will not be imputed for analysis of exploratory efficacy endpoints.

### **8.5.1. Missing eGFR for Sensitivity Analyses**

Multiple imputation is the primary approach used to account for missing data in sensitivity analyses of the primary efficacy endpoints (i.e., Week 48 and Week 100) and the key secondary endpoints (i.e., Week 52 and Week 104). Results of sensitivity analyses are summarized in tables and forest plots.

### **8.5.2. Missing eGFR for MMRM Analyses**

The primary analysis of efficacy endpoints is based on the assumption of missing at random (MAR). Missing data are not imputed for the primary analysis of eGFR where the analysis method is defined as MMRM (i.e., Week 48 and Week 100) (Section 6.6.1.1).

### **8.5.3. Missing eGFR for ANCOVA Analyses**

Missing eGFR data are imputed using multiple imputation for the primary analysis of eGFR where the analysis method is defined as ANCOVA (i.e., Week 52 and Week 104) (Section 6.6.1.2). For the primary analysis, multiple imputation is based on the treatment group to which the subject is assigned. A tipping point analysis is used to assess the validity of the MAR assumption.

## **8.6. Year 1: Primary Efficacy Endpoint**

The analyses of the primary and key secondary endpoints are described in Sections 8.6 and 8.7. Additional details and pseudo SAS code are provided in a separate document.

### **8.6.1. Primary Analysis of the Year 1 Primary Efficacy Endpoint**

The Year 1 primary endpoint of this study is the change in eGFR at Week 48 (i.e., the end of the first year of drug exposure). The change from baseline eGFR for patients treated with bardoxolone methyl is compared with placebo at Week 48 using mixed models repeated measures (MMRM) analysis, with baseline eGFR (BASE\_eGFR), ACR strata (ACR\_STRAT), and fraction of one-year exposure to treatment (TRT\_EXP1) as covariates and the following fixed factors: treatment group (TRT), time (i.e., VISIT; analysis visit number), the interaction between treatment and time (TRT x VISIT), and the interaction between baseline eGFR and time (BASE\_eGFR x VISIT) as covariates. Inclusion of the fraction of expected one-year exposure to treatment (Section 6.5.11) in the MMRM model as a covariate provides an adjustment for eGFR values collected from early discontinuation patients having less than 1-year of drug exposure.

The trial design separates discontinuation of study drug from discontinuation of study follow-up. Therefore, patients may discontinue early from study drug while continuing follow-up with study visits and assessments. The primary analysis of eGFR at Week 48 uses available eGFR values irrespective of whether or not a patient is receiving treatment. The MMRM analysis uses all eGFR values collected through Week 48 according to analysis visits 0, 1, 2, 4, 6, 8, 12, 24, 36, and 48 (Section 6.5.4). An unstructured covariance matrix is used.

In the event the MMRM model with an unstructured covariance structure does not converge, the following covariance structures are substituted, in the order listed. Each subsequent covariance structure is used only if each previous covariance structure is used and no previous model converged.

1. Heterogeneous Toeplitz covariance structure (assuming different variances at each time point and that measurements taken closer together in time are more highly correlated than those taken farther apart).
2. Toeplitz covariance structure (assuming measurements taken closer together in time are more highly correlated than those taken farther apart).
3. First order auto-regressive [AR(1)] covariance structure (assuming measurements taken closer together in time are more highly correlated than those taken farther apart, but the correlation is more constrained than the Toeplitz structure).
4. Compound symmetry covariance structure (assuming equal correlation for measurements from a patient, regardless of how far apart in time they were taken). A compound symmetry covariance structure was assumed in the sample size calculation.

The difference between bardoxolone methyl and placebo in change from baseline of eGFR is estimated along with the 95% confidence interval at Week 48 for the primary analysis of the Year 1 primary endpoint.

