#### 4.4.3. No Changes Due to Temporary Interruptions in Study Treatment

A COVID-19 appendix was added to the study protocol to allow for temporary interruptions in study treatment. No changes are required for analyses of Week 100 or Week 104 due to temporary discontinuation and reinitiation of study drug given how the key efficacy analyses were defined:

- Analyses of Week 100 are based on target study day, irrespective of whether or not a patient is receiving study drug.
- Analyses of Week 104 are based on days after final dose following permanent study drug discontinuation in the second year. Analyses of Week 104 data will not include data collected during any intermediate off-treatment period.

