#### **6.3.1. ITT Population**

The intent-to-treat analysis set is defined as all enrolled patients categorized by their randomized treatment group (whether or not they received study drug). Note that this is the same definition for both the Year 1 and Year 2 analyses.

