#### **6.5.11. Exposure Duration**

Exposure duration is used in analysis of efficacy to adjust analysis of off-treatment eGFR for the exposure duration within each year. Fraction of expected exposure duration is calculated for the first and second years of treatment as follows:

- First year exposure (TRT\_EXP1) =  
[(date of last dose in first year) – (date of first dose)]/336
- Second year exposure (TRT\_EXP2) =  
[(date of last dose in second year) – (date of first dose)]/700

where 336 is the number of days in the first year (i.e., 48-week) treatment interval, and 700 is the number of days in the second year (i.e., 100-week) treatment interval. Exposure in the second year is simply total exposure and does not subtract the 4-week off-treatment period at the end of the first year.

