## 8. PRIMARY EFFICACY

Analyses of efficacy described in this section are the primary analyses of the Phase 3 efficacy endpoints, and pertain to the ITT population (i.e., all patients randomized in the Phase 3 portion of the study). The trial includes endpoints following one and two years of treatment. Additional details regarding the statistical approach and pseudo SAS code are available in the programming conventions document.

The following abbreviations are used in descriptions of the analysis models:

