### 8.2. Statement of the Null and Alternate Hypotheses

All primary and key secondary efficacy endpoints compare the change from baseline in eGFR for patients randomized to bardoxolone methyl ( $\mu_{\text{BARD}}$ ) to the change from baseline in eGFR for patients randomized to placebo ( $\mu_{\text{placebo}}$ ) at the endpoint-specified visit according to the following hypotheses:

- $H_0: (\mu_{\text{BARD}}) - (\mu_{\text{placebo}}) = 0 \text{ mL/min/1.73 m}^2$
- $H_1: (\mu_{\text{BARD}}) - (\mu_{\text{placebo}}) \neq 0 \text{ mL/min/1.73 m}^2$

Because eGFR decreases with disease progression, an increase in eGFR relative to placebo is considered evidence of benefit.

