### **8.8.1. Primary Analysis of the Year 2 Primary Efficacy Endpoint**

The Year 2 primary endpoint of this study is the change in eGFR at Week 100 (i.e., the end of the second year of exposure). The change from baseline in eGFR for patients treated with bardoxolone methyl is compared with placebo at Week 100 using the statistical model defined in Section 8.6.1 with the following modifications:

- The analysis uses all eGFR values collected through Week 100 according to analysis visits 0, 1, 2, 4, 6, 8, 12, 24, 36, 48, 64, 76, 88, and 100 (Section 6.5.4).
- TRT\_EXP2 is added as a covariate and TRT\_EXP1 is removed.

Inclusion of the fraction of expected two-year exposure to treatment (TRT\_EXP2; Section 6.5.11) in the MMRM model as a covariate provides an adjustment for eGFR values collected from early discontinuation patients having less than 2-years of drug exposure. All eGFR values collected in the Week 52 analysis window assess the effect following 4-weeks of drug withdrawal and therefore are not included in the MMRM analysis of Week 100.

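### The Week 48 and Week 100 primary MMRMs adjust for time on drug, a post-randomisation variable, so their treatment difference can depart from the ITT comparison the SAP describes

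*SAP*

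**What the plan says.** **The comparison described.** SAP 6.3.1 defines the ITT set as "all enrolled patients categorized by their randomized treatment group (whether or not they received study drug". Section 8 says the primary efficacy analyses "pertain to the ITT population (i.e., all patients randomized in the Phase 3 portion of the study". Under 8.2 the primary and key secondary hypotheses "compare the change from baseline in eGFR for patients randomized to bardoxolone methyl" with the same change on placebo. On data, 8.6.1 states: "The primary analysis of eGFR at Week 48 uses available eGFR values irrespective of whether or not a patient is receiving treatment". The SAP addendum, 4.4.3, says the same for Year 2: "Analyses of Week 100 are based on target study day, irrespective of whether or not a patient is receiving study drug".

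**The model specified.** The Week 48 MMRM (8.6.1) includes TRT_EXP1, which "as a covariate provides an adjustment for eGFR values collected from early discontinuation patients having less than 1-year of drug exposure". The Week 100 MMRM (8.8.1) replaces it with TRT_EXP2, which "provides an adjustment for eGFR values collected from early discontinuation patients having less than 2-years of drug exposure". SAP 6.5.11 gives both as last-dose date minus first-dose date, divided by 336 or 700. Addendum 3.1 keeps TRT_EXP2 but uses the last dose in the study, adds one day and divides by 707. TRT_EXP2 also enters the Week 100 PGIC and CGI-I models (9.2, 9.3), which are in the alpha-controlled Year 2 sequence (8.4).

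Section 6.5.11 describes exposure duration as an adjustment for off-treatment eGFR. The Week 48 and Week 100 MMRMs go beyond that purpose.

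**The concern.** Exposure is an outcome of the randomised treatment as well as a patient characteristic. Holding it fixed compares the arms at equal time on drug, not as randomised. The listed model has no interaction of exposure with treatment or visit, so one slope serves both arms and every visit. A patient's Week 1 value is adjusted for when that patient later stops, and in the placebo arm the term measures time on placebo.

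If patients with worse prognosis tend to stop, the slope is positive and the adjustment favours whichever arm stops more.

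The primary tests of both years rest on this estimate, and the SAP names no estimand. The planned analyses do not show how much the term contributes:

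- The tipping-point and as-treated analyses reuse the 8.6.1 model.
- The per-protocol analysis also reuses it. Its population must have received drug through Week 48 or Week 100, so the term is nearly constant there, but that set is not ITT.
- No outcome model is named for the control-based imputation of the primary endpoints.
- The term is absent only from descriptive summaries (8.1) and from exploratory categorical and distribution analyses (9.1.2, 9.1.3). None of these is a model-based ITT estimate of the mean difference.

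**Working it through.** **1. The plan's own figures, for scale.** Inputs from SAP 4.3.1: 78 and 79 patients, SD 8, correlation 0.7, two-sided alpha 0.025. The stated power reproduces when the difference is averaged over m visits: SE = 8 × √[(1 + 0.7(m − 1))/m] × √(1/78 + 1/79).

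- Week 48, m = 9: SE 1.09; power at 3.4 is 80.7% (normal) or 80.0% (t).
- Week 100, m = 13: SE 1.09; power at 3.3 is 78.8% or 78.0%.

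Both agree with the stated figure of about 80%. No exposure term enters the power calculation.

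**2. The mechanism.** With γ the fitted exposure slope and the other terms unchanged:

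adjusted difference − unadjusted difference = −γ × (mean exposure on drug − mean exposure on placebo).

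A generalised least squares MMRM confirmed this (9 visits, compound symmetry, 200,000 simulated patients per arm, complete follow-up):

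| Stopping, drug v placebo | On-drug effect | Stopping related to prognosis | Without term | With term |
|---|---|---|---|---|
| 20% v 20% | 3.4, lost on stopping | no | 2.70 | 2.70 |
| 20% v 10% | 3.4, lost on stopping | no | 2.72 | 2.79 |
| 30% v 10% | 3.4, lost on stopping | no | 2.40 | 2.56 |
| 30% v 10% | 3.4, lost on stopping | yes | 2.39 | 2.92 |

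In the last row γ = 5.30 and the gap is −0.099, so the shift is 5.30 × 0.099 = 0.52, against 0.53 fitted. With no drug effect and prognosis-related stopping, the shifts were +0.12 to +0.37.

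**3. Trial-sized simulation.** These inputs are assumptions; the documents give no rates.

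- Scenario (a): random stopping of 20% on drug and 5% on placebo, plus the worst-prognosis 10% of each arm. Total stopping is 0.10 + 0.90 × 0.20 = 28% v 0.10 + 0.90 × 0.05 = 14.5%.
- Scenario (b): 25% and 5%, plus the worst 15%. Total stopping is 36% v 19%.
- Exposure is 1 for completers and uniform on 0.05 to 0.95 for stoppers. The gap in (a) is (0.28 − 0.145) × 0.5 = 0.068.
- Prognosis correlates 0.6 with the last-visit outcome. Baseline covariates explain half of prognosis, or none of it as an upper bound.
- The MMRM is likelihood-based with unstructured covariance. Ranges run from prognosis that builds up over time to constant prognosis.

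Worked example, (a), constant prognosis: slope 3.5 × 0.068 = 0.24 with half explained; slope 6.6 × 0.068 = 0.45 with none explained. A separate single-visit ANCOVA check also gave +0.24 and +0.45 for (a), and +0.33 and +0.60 for (b).

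No drug effect (shift in mL/min/1.73 m2; rejection at 0.025):

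| Week 48 case | (a) | (b) | Rejection with term, (a); (b) | Rejection without |
|---|---|---|---|---|
| Half explained, complete data | +0.05 to +0.23 | +0.07 to +0.32 | 2.4–3.0%; 2.7–2.9% | 2.3–2.8% |
| Half explained, half of stoppers lost | +0.04 to +0.22 | +0.05 to +0.31 | – | – |
| None explained, complete data | +0.07 to +0.44 | +0.09 to +0.60 | 2.8–4.0%; 2.6–3.6% | 2.4–2.9% |

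The Monte Carlo SE of a rejection rate is about 0.2 to 0.35 points. Equal stopping, or stopping unrelated to prognosis, gives 0.00. More stopping on placebo gives −0.05 to −0.33. Week 100 (13 visits, half explained) gives +0.05 to +0.24 in (a) and +0.06 to +0.32 in (b).

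Drug effect of 4.0 lost on stopping, Week 48, half explained:

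| Case | True ITT | Without term | With term | Rejection without / with |
|---|---|---|---|---|
| (a) complete data | 4.0 × 0.72 = 2.88 | 2.87–2.89 | 3.00–3.24 | 55–56% / 60–68% |
| (b) complete data | 2.55 | 2.54–2.55 | 2.72–2.99 | 45% / 52–62% |
| (a) half of stoppers lost | 2.88 | 3.35–3.39 | 3.43–3.68 | – |
| (b) half of stoppers lost | 2.55 | 3.12 | 3.22–3.50 | – |

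For PGIC with no drug effect, assuming SD 1.34 and correlation 0.6 with prognosis, the shift is 0.04 to 0.07 points in (a) and 0.05 to 0.10 in (b), in favour of the arm that stops more.

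**The case against.** The strongest reply has five parts.

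- **The adjustment is declared and explained.** Every randomised patient stays in the assigned arm, and no passage promises an estimate free of exposure adjustment. This is true, but keeping the ITT set does not make the contrast ITT. The stated reason, adjusting for early stoppers, describes the departure rather than removing it.
- **The harm under the null is small.** With half of prognosis explained, the shift is 0.05/3.4 = 1.5% to 0.32/3.4 = 9.4% of the powered effect, and at most a quarter of a single-visit SE (8 × √(1/78 + 1/79) = 1.28). Rejection rates are barely distinguishable. This stands, so the case rests on the estimate and its interpretation, not on inflated type I error.
- **The scenarios are harsh.** Total stopping is 28% or 36% on drug, and in (a) the whole worst-prognosis tenth stops, averaging about 1.755 × 0.6 × 8 = 8.4 below the mean. No document supports these inputs. This stands as a limit on size, not on the mechanism.
- **Dropping the term does not cure missing data.** In (a) with half of stoppers lost, missingness adds about 0.5 and the term a further 0.08 to 0.29. This also stands.
- **Some material is not available.** The protocol supplied is only its COVID-19 addendum, and model code sits in a separate document. What is said here to be absent is therefore absent from the SAP and its addendum. The allowance in 8.6.2 for further sensitivity analyses commits the sponsor to nothing.

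**Conclusion.** The concern holds. Both primary MMRMs condition on a variable determined after randomisation, so the reported difference can depart from the ITT comparison the SAP describes. No planned model-based ITT estimate would reveal by how much.

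The mechanism is certain; the size and direction in this trial are not. The shift is zero when mean exposure is equal between arms, or when exposure is unrelated to eGFR change given the other terms. It favours the drug only if the drug arm stops more and stoppers do worse. The figures above rest on assumed stopping rates and prognosis. On those assumptions the distortion is modest under the null and larger when a real effect is lost on stopping: +0.12 to +0.36 in (a) and +0.17 to +0.44 in (b) with complete data. It should be fixed.

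Weeks 52 and 104 are not challenged. There the term partly stands in for unequal measurement times.

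**What to change.** - **Primary models:** remove TRT_EXP1 from 8.6.1 and TRT_EXP2 from 8.8.1. Keep baseline eGFR, ACR stratum and, at Week 100, the region term from addendum 4.4.2. Remove TRT_EXP2 from the Week 100 PGIC and CGI-I models in 9.2 and 9.3.
- **Estimand:** state that it is treatment-policy, and report the exposure-adjusted model as supplementary.
- **If Year 1 is already unblinded (5.1):** keep the planned Week 48 result and report the model without the term beside it.
- **If the Year 2 primary model can no longer change without an integrity concern:** prespecify the Week 100 ITT MMRM without the term before the Year 2 lock, and report both side by side.
- **Missing off-drug eGFR:** leave this to the existing sensitivity analyses; removing the term does not address it.
- **Weeks 52 and 104:** leave the visit rules and endpoints unchanged; add only a report with and without the exposure term.

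The cost is SAP wording, one model term, and one extra run each for Weeks 52 and 104, with no new data or visits. In the simulations, removing the term changed the standard error by −1% to +2%. The estimate may be less favourable.

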#### 4.3.1. Primary Endpoints

With 157 patients enrolled (78 in one group and 79 in the second group), the study will have approximately 80% power to detect a difference between the two treatment groups in change from baseline in eGFR of 3.4 mL/min/1.73 m^2 for the primary endpoint at Week 48 in Year 1. The power calculation for Year 1, which was based on mixed-model repeated measures (MMRM) analysis, assumes the following:

- 9 repeated measurements (Weeks 1, 2, 4, 6, 8, 12, 24, 36, and 48) having compound symmetry covariance structure
- The correlation between observations on the same subject is 0.7
- Two-sided Type I error rate of 0.025
- Standard deviation of change from baseline in eGFR of 8 mL/min/1.73 m^2
- Analyses at Week 48 are based on the intent-to-treat (ITT) population

Analysis of the Year 2 primary endpoint, which also will use the ITT population, will have approximately 80% power to detect a difference of 3.3 mL/min/1.73 m^2 assuming 13 repeated measurements, a correlation of 0.7 between observations, a standard deviation of 8 mL/min/1.73 m^2, and a two-sided type I error rate of 0.025. The primary analysis of efficacy will use an unstructured covariance structure, which is expected to have approximately the same power as the analysis with compound symmetry used for study planning.

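### Three of the four fallback covariance structures for the primary MMRM impose one variance at every visit, so if they are reached and the SD rises with follow-up, the Week 48 or Week 100 standard error is too small

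*SAP*

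**What the plan says.** SAP Section 8.6.1 makes the unstructured matrix the primary choice and lists four replacements. Each is used only if no earlier model in the list has converged.

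- Step 1, heterogeneous Toeplitz, is the only one described as letting the variance differ between time points.
- Step 2 is "Toeplitz covariance structure (assuming measurements taken closer together in time are more highly correlated than those taken farther apart".
- Step 3, AR(1), is described in the same terms with a more constrained correlation.
- Step 4 is "Compound symmetry covariance structure (assuming equal correlation for measurements from a patient, regardless of how far apart in time they were taken".

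Time enters the model as the analysis visit number. Section 8.8.1 carries the model to Year 2: "The analysis uses all eGFR values collected through Week 100 according to analysis visits 0, 1, 2, 4, 6, 8, 12, 24, 36, 48", followed by Weeks 64, 76, 88 and 100. Gaps between post-dose visits run from 1 week to 16 weeks.

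The planning figures in Section 4.3.1 are "Standard deviation of change from baseline in eGFR of 8 mL/min/1.73 m", with no SD by visit, and "The correlation between observations on the same subject is 0.7". Neither section mentions an empirical (sandwich) standard error. Sections 8, 8.6 and 8.8 refer further model detail to a separate document that was not supplied.

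**The concern.** Each primary endpoint is a treatment contrast at one late visit. A structure with a common variance bases the standard error of that contrast on a variance pooled over all visits, and 6 of the 13 post-dose visits in the Year 2 model fall in Weeks 1 to 12. If change from baseline is less variable early than late, the pooled variance is smaller than the variance at the endpoint visit. The standard error is then too small and the test rejects too often. These tests carry the error control claimed in Section 8.4, and pre-specifying a fallback does not restore its type I error.

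Three features of the SAP make equal variance an unsafe default.

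- The authors themselves chose unstructured first and a heterogeneous structure second.
- Section 12.1 expects off-treatment eGFR to vary differently, while the primary analysis uses values whether or not the patient is on drug.
- Analysis visit 0 is listed in the model, and Day 1 eGFR makes up half of baseline (Section 6.4.1), so change at that visit should vary little.

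A smaller, separate point concerns wording. Heterogeneous Toeplitz, Toeplitz and AR(1) set correlation by visit order. Weeks 1 and 2 therefore get the same correlation as Weeks 48 and 64, and a description in terms of closeness in time is not accurate for this schedule.

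**Working it through.** **Inputs from the SAP.** "With 157 patients enrolled (78 in one group and 79 in the second group), the study will have approximately 80% power"; "Two-sided Type I error rate of 0.025" (critical value z = 2.2414); SD 8; correlation 0.7; visits as listed in Sections 8.6.1 and 8.8.1.

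**Step 1: reproduce the planning figure.** Under compound symmetry the SD of the mean over m visits is 8 × √[(1 + (m − 1) × 0.7)/m], and its standard error is that SD × √(1/78 + 1/79).

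- Year 1, m = 9: SD 6.851, SE 1.094. 3.4/1.094 − 2.241 = 0.868, so power is 80.7%.
- Year 2, m = 13: SD 6.803, SE 1.086. 3.3/1.086 − 2.241 = 0.798, so power is 78.7%.

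Both agree with the stated figure of approximately 80%, read as a difference averaged over visits. Planning therefore rests on one SD of 8 and equal correlation.

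**Step 2: compound symmetry with complete data.** The fitted variance equals the mean of the visit variances. Hence SE ratio = √(mean visit variance) / (SD at the endpoint visit), and actual type I error = 2 × [1 − Φ(2.2414 × ratio)]. The SD is assumed to change linearly in weeks from Week 1 to the endpoint visit. These paths are assumptions, not figures from the documents.

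| Endpoint | Assumed SD | Mean variance | Its root | Ratio | Actual error at nominal 0.025 |
|---|---|---|---|---|---|
| Week 100 | 8 throughout | 64.00 | 8.000 | 1.000 | 0.025 |
| Week 100 | 7 to 9 | 59.90 | 7.739 | 0.860 | 0.054 |
| Week 100 | 6 to 8 | 45.48 | 6.744 | 0.843 | 0.059 |
| Week 48 | 6 to 8 | 44.33 | 6.658 | 0.832 | 0.062 |
| Week 100 | 10 to 8 | 86.80 | 9.317 | 1.165 | 0.009 |

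For SD 6 to 8 at Week 100, the true standard error is 8 × √(1/78 + 1/79) = 1.277 and the model reports 6.744 × √(1/78 + 1/79) = 1.076. If alpha is recycled so that Year 2 is tested at 0.05 (SAP addendum, Section 3.2), SD 7 to 9 gives 2 × [1 − Φ(1.960 × 0.860)] = 0.092.

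**Step 3: all three common-variance structures.** Each structure was fitted by large-sample maximum likelihood, and the model-based standard error was compared with the true one. Assumed conditions: true correlation either 0.7 throughout or decaying in real time, and dropout of 0% or 20% completely at random over the last four visits. Ranges cover Toeplitz, AR(1) and compound symmetry at both endpoints.

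| Assumed SD | SE ratio | Actual error at nominal 0.025 |
|---|---|---|
| 8 throughout | 0.97 to 1.02 | 0.023 to 0.030 |
| 6 to 8 | 0.80 to 0.86 | 0.055 to 0.072 |
| 5 to 8 | 0.72 to 0.78 | 0.079 to 0.106 |
| 10 to 8 | 1.13 to 1.20 | 0.007 to 0.012 |

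**Step 4: visit spacing alone.** The first row of the Step 3 table isolates spacing: with SD flat at 8, the standard error moves by about 3% or less, mainly when data are missing. Heterogeneous Toeplitz gave a ratio of 1.00 under equal correlation. When correlation decays in real time it gave 1.10 to 1.13, which is conservative.

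**Step 5: visit 0.** If visit 0 is fitted as a response with an assumed SD of 1 to 4, and all other visits have SD 8, the ratio is 0.92 to 0.97 and the error 0.029 to 0.038.

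**The case against.** The strongest reply is that the trigger is remote. The harmful structures are reached only after two failures, and the second must be of a model that already has visit-specific variances. For 13 visits the unstructured matrix has 13 × 14/2 = 91 parameters. Heterogeneous Toeplitz has 13 + 12 = 25, for 157 patients, and nothing in the documents suggests that it would fail. This stands, and it sets the priority.

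The size is also assumed. Section 4.3.1 uses 8 for both years, a flat SD does essentially no harm, and a falling SD makes the test conservative. This stands too. The separate programming document might name a robust standard error, so its absence can be asserted only of the supplied text.

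Three stronger readings are tempting and should not be drawn.

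- *That the same three structures also treat the visits as equally spaced.* Compound symmetry uses no spacing at all. The structures indexed by visit order are heterogeneous Toeplitz, Toeplitz and AR(1).
- *That unequal spacing drives the understated standard error.* Step 4 shows that it does not; the equal-variance constraint does.
- *That subgroup and Japanese-population fits put error control at risk.* Section 8.3 makes subgroup p-values descriptive, Section 6.3.5 makes the Japanese analysis a sensitivity analysis, and Section 8.4 gives neither any alpha. No subgroup sizes are given from which to judge whether those fits would fail to converge.

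An uncorrected sandwich standard error is itself anti-conservative in small samples. In a simulated last-visit ANCOVA with constant variance and complete data, at nominal 0.025, it gave type I error of about 0.061 with 10 per arm and 0.037 with 20 per arm, against 0.026 and 0.023 for the model-based test. With 78 per arm it gave 0.028. The remedy must therefore distinguish the full population from small subsets.

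**Conclusion.** The point holds in conditional form. Fallbacks 2 to 4 impose a common variance, and the supplied text offers no protection against its being wrong. Three things must coincide for harm: the unstructured fit fails, the heterogeneous Toeplitz fit fails, and the SD of change rises with follow-up. In that case a nominal 0.025 test has type I error of about 0.05 for an SD rising from 7 to 9, and about 0.06 to 0.07 for 6 to 8. Steeper rises do more damage. These figures rest on assumed SD paths.

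A reader might infer that the primary result as planned is anti-conservative. The documents do not support that: the planned model is unstructured, and its first replacement allows unequal variances. The spacing issue is an error of description with little numerical effect on the common-variance structures. This is a low-priority improvement to a contingency rule.

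**What to change.** In Section 8.6.1, keep heterogeneous Toeplitz as the first fallback. Replace the remaining three with heterogeneous AR(1), or spatial power in weeks with visit-specific variances, and then heterogeneous compound symmetry. For 13 visits, heterogeneous AR(1) and heterogeneous compound symmetry each need 13 variances plus one correlation, 14 parameters against 25, so they are simpler to fit without giving up unequal variances.

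State that the full-population Week 48 and Week 100 analyses are reported with an empirical (sandwich) standard error whenever a structure other than unstructured is used. For subgroup and Japanese-population fits, use the same heterogeneous structures with model-based or small-sample-corrected standard errors, not an uncorrected sandwich.

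Reword the descriptions so that Toeplitz-type and AR(1) correlation is said to depend on visit order, and only a spatial structure on elapsed time. Section 8.8.1 inherits these changes by reference.

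The cost is a few lines of SAP text, a model option, and a slightly noisier standard error if a fallback is used.
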